The ATD phase in Arm 1, Arm 2, and Arm 3 will have single-subject cohorts, but may allow up to 3 subjects per cohort to account for simultaneous enrollment. During MK-1454 dose escalation in Arm 1 (Parts A and B), Arm 2 (Parts C and D), and Arm 3 (Parts E and F), there will be at least 7 days of observation between each of the first 2 subjects at each dose level. Dose escalation of MK-1454 to determine the MTD/MAD for all 3 treatment arms will be guided by the mTPI design, targeting a DLT rate of 30%. Doses of MK-1454 used in combination with pembrolizumab will be at least 2 dose levels behind the monotherapy MK-1454 dose and will not exceed the MTD for monotherapy. If an MTD for the monotherapy arm is established, then the dose of MK-1454 in combination may continue escalation up to that dose. For example, if the MTD for monotherapy (Arm 1, Part A) is , then the starting dose for combination therapy (Arm 2, Part C), if no DLTs occurred in monotherapy, may be with a maximum dose escalation to . If the MTD for monotherapy (Arm 1, Part A) is cel then the starting dose for combination therapy will In monotherapy (Arm 1, Part A), if the dose level is completed, then the starting dose in combination therapy (Arm 2, Part \overline{C}) will be

Once a dose level in the mTPI phase has been cleared for DLT, and a decision made to escalate to the next dose level, the cohort may be expanded to a total of 14 subjects to obtain additional pharmacokinetic and pharmacodynamics data. Dose-limiting toxicity information from these "back-filling" cohorts will not be formally included in the mTPI analysis for MTD determination but will be taken into consideration for preliminary RP2D determination. For each new dose level in the mTPI phase, there may be a minimum of 3 subjects and up to 6 subjects per cohort. Based on the occurrence of DLTs, up to 14 subjects may enroll per dose level. Therefore, during mTPI, up to 14 subjects may be enrolled per dose level, depending on the occurrence of a DLT. Subjects may continue their assigned treatment for up to 35 cycles (approximately 2 years) from the start of treatment.

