The number of subjects who are enrolled at each dose is capped to minimize the exposure to a dose that may be unacceptably toxic (denoted as DU in Table 10). To find out how many more subjects may be enrolled, count steps in a diagonal direction (down and to the right) from the cell (3 subjects, 1 DLT) to the first cell marked DU. For example, if 1/3 of the subjects have experienced a DLT at a given dose level, then no more than an additional 3 subjects should be enrolled at this dose level until additional DLT data are available. This is because this dose level would be considered unacceptably toxic if all 3 of the additional subjects experience a DLT (ie, 4/6 subjects with DLT in Table 10).

De-escalation (D) or excluding the dose from the trial due to unacceptable toxicity (DU) at the starting dose level of Arm 1 of the study indicates stopping of the trial. Escalation (E) at the highest dose level indicates staying at that level. During dose escalation and confirmation, it may be acceptable to de-escalate to an intermediate, not predefined and not

Protocol/Amendment No.: 001-08

previously-studied dose if evaluation of toxicity at such a dose is desired. If this approach is taken, 3-6 new subjects may be enrolled at the new intermediate dose, and the aforementioned rules should be used to determine further enrollment at this dose level. After 14 subjects have been enrolled at any of the tested doses (including intermediate doses), dose finding will stop if the mTPI table indicates "S" for staying at current dose. Otherwise, up to 14 new subjects may be enrolled at a lower dose if "D" or "DU" is indicated, or at a higher dose if "E" is indicated. Establishment of the MTD/MAD for the combination of MK-1454 and pembrolizumab in Arm 2 requires that at least half of the 14 subjects in the MTD/MAD cohort have had no prior exposure to MK-1454 (ie, non-crossover subjects). Priority for enrollment in the MTD/MAD confirmation cohort of Arm 2 will be given to MK-1454-naïve subjects.

While the mTPI design is applied separately to Arm 1 and Arm 2, doses of MK-1454 used in combination with pembrolizumab via cutaneous or subcutaneous IT injection will be at least 2 dose levels behind the MK-1454 monotherapy dose, and will not exceed the MTD for monotherapy. If an MTD for monotherapy (Arm 1) is established, then the dose of MK-1454 in Arm 2 may continue escalation up to that established dose.

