For Arm 3, dose escalation will proceed by incrementing dose frequency then dosage level. The initial dose frequency of visceral IT will be collected. Per mTPI design, frequency will increase in the next cohort to collected for 2 cycles, followed by thereafter. Further increase in visceral IT injection frequency to collected for 2 cycles, followed by thereafter in a subsequent cohort will be based on mTPI design. After Cycle 3, the frequency of visceral IT administration may be modified based on clinical assessment of safety by the investigator in consultation with Sponsor. Dose decisions will be made jointly with the investigators. Enrollment into Arm 3 will be monitored through IWRS.

Protocol/Amendment No.: 001-08

Table 10 Dose-finding Rules per mTPI Design

	Num	Number of subjects evaluable for DLT at current dose										
Number of subjects with at												
least 1 DLT	3	4	5	6	7	8	9	10	11	12	13	14
0	Е	Е	Е	Е	Е	Е	Е	Е	Е	Е	Е	E
1	S	S	S	Е	Е	Е	Е	Е	Е	Е	Е	E
2	D	S	S	S	S	S	S	S	Е	Е	Е	E
3	DU	DU	D	S	S	S	S	S	S	S	S	S
4		DU	DU	DU	D	D	S	S	S	S	S	S
5			DU	DU	DU	DU	DU	D	S	S	S	S
6				DU	DU	DU	DU	DU	DU	D	S	S
7					DU	D						
8						DU						
9							DU	DU	DU	DU	DU	DU
10								DU	DU	DU	DU	DU
11									DU	DU	DU	DU
12										DU	DU	DU
13											DU	DU
14												DU

D = De-escalate to the next lower dose

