5.2.7 Replacement of Subjects During the DLT Evaluation Period

Subjects discontinuing within 21 days of the first dose due to reasons unrelated to study treatment will not be considered evaluable for DLTs and may be replaced. Subjects with a DLT within 21 days of the first dose should not be replaced. See Section 8.5.1 for description of safety analysis population.

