5.8.1 Discontinuation of Treatment

Discontinuation of treatment does not represent withdrawal from the trial.

As certain data on clinical events beyond treatment discontinuation may be important to the study, they must be collected through the subject's last scheduled follow-up, even if the subject has discontinued treatment. Therefore, all subjects who discontinue trial treatment prior to completion of the treatment will still continue to participate in the trial as specified in Section 6.0 - Schedule of Activities and Section 7.1.5.4 – Discontinued Subjects Continuing to be Monitored in the Trial.

Subjects may discontinue treatment at any time for any reason or be dropped from treatment at the discretion of the investigator should any untoward effect occur. In addition, a subject may be discontinued from treatment by the investigator or the Sponsor if treatment is inappropriate, the trial plan is violated, or for administrative and/or other safety reasons. Specific details regarding procedures to be performed at treatment discontinuation are provided in Section 7.1.4 – Other Procedures.

A subject must be discontinued from treatment but continue to be monitored in the trial for any of the following reasons:

- The subject or subject's legally acceptable representative requests to discontinue treatment.
- o Confirmed radiographic disease progression outlined in Section 7.1.2.7 (exception if the Sponsor approves treatment continuation).

27-Jul-2021 Confidential

087V73

Protocol/Amendment No.: 001-08

o The subject interrupts trial medication administration for more than 12 consecutive weeks.

- o Any progression or recurrence of any malignancy, or any occurrence of another malignancy that requires active treatment.
- o Intercurrent illness other than another malignancy as noted above that prevents further administration of treatment.
- o Recurrent Grade 2 pneumonitis.
- The subject is noncompliant with the protocol.
- The subject has a medical condition or personal circumstance which, in the opinion of the investigator and/or Sponsor, placed the subject at unnecessary risk from continued administration of study drug.
- The subject has a confirmed positive serum pregnancy test.
- O Side effects and/or concomitant medications required for treatment of HIV and/or its complications that are incompatible with continued study treatment (exceptions are permissible but should be discussed with the Sponsor).

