7.2 Assessing and Recording Adverse Events

An AE is defined as any untoward medical occurrence in a patient or clinical investigation subject administered a pharmaceutical product and which does not necessarily have to have a causal relationship with this treatment. An AE can therefore be any unfavourable and unintended sign (including an abnormal laboratory finding, for example), symptom, or disease temporally associated with the use of a medicinal product or protocol-specified procedure, whether or not considered related to the medicinal product or protocol-specified procedure. Any worsening (i.e., any clinically significant adverse change in frequency and/or intensity) of a preexisting condition that is temporally associated with the use of the Sponsor's product, is also an AE.

Changes resulting from normal growth and development that do not vary significantly in frequency or severity from expected levels are not to be considered AEs. Examples of this may include, but are not limited to, teething, typical crying in infants and children and onset of menses or menopause occurring at a physiologically appropriate time.

Sponsor's product includes any pharmaceutical product, biological product, device, diagnostic agent or protocol-specified procedure, whether investigational (including placebo or active comparator medication) or marketed, manufactured by, licensed by, provided by or distributed by the Sponsor for human use.

AEs may occur during clinical trials, or as prescribed in clinical practice, from overdose (whether accidental or intentional), from abuse and from withdrawal.

Progression of the cancer under study is not considered an AE.

All AEs that occur after consent is documented but before treatment allocation/randomization must be reported by the investigator if they cause the subject to be excluded from the trial, or are the result of a protocol-specified intervention, including but not limited to washout or discontinuation of usual therapy, diet, placebo treatment or a procedure. From the time of treatment allocation/randomization through 30 days following cessation of treatment, all AEs must be reported by the investigator. Such events will be recorded at each examination on the AE CRFs/worksheets. The reporting timeframe for AEs meeting any serious criteria is described in section 7.2.3.1. The investigator will make every attempt to follow all subjects with nonserious adverse events for outcome.

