8.5.1 Safety Analysis Population

The ASaT population will be used for the analysis of safety data in this study. The ASaT population consists of all subjects who received at least one dose of study treatment. In case

Protocol/Amendment No.: 001-08

of treatment administration errors, subjects will be analyzed according to the treatment they actually received. The DLTe population includes ASaT subjects that were observed for safety for 21 days after the first dose of assigned treatment or experienced a DLT prior to 21 days after the first dose of assigned treatment. The replacement subjects will also be considered evaluable if the above specified criteria are met.

At least one laboratory or vital sign measurement obtained subsequent to at least 1 dose of study treatment is required for inclusion in the analysis of each specific parameter. To assess change from baseline, a baseline measurement is also required.

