8.6.2 Statistical Methods for Safety Analyses

Safety and tolerability will be assessed by clinical review of all relevant parameters including AEs, SAEs, laboratory tests, vital signs, ECG measurements, and physical examinations.

MK-1454-001-08 Final Protocol 27-Jul-2021 Confidential

Protocol/Amendment No.: 001-08

AEs will be summarized by counts and frequencies for each dose level, arm, and cohort. Laboratory tests, vital signs, and other safety endpoints will be summarized as appropriate.

Dose-limiting toxicities will be listed, and further summarized by dose level and arm. The pool adjacent-violators-algorithm [31], which forces the DLT rate estimates to be nondecreasing with dose levels and pools adjacent violators for weighted estimates by sample size, will be used to estimate the DLT rates across doses in each treatment arm. The estimates of the DLT rates among subjects treated at the MTDs (or MADs) and the 80% Bayesian credible intervals based on a prior distribution of Beta (1,1) for the estimates will be provided.

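### Section 8.5.1 counts a DLT-free subject as DLT-evaluable after 21 days of observation, with no minimum Cycle 1 MK-1454 exposure, and its fit with Section 5.2.7 is unclear

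*Combined protocol and SAP*

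**What the plan says.** **Who is evaluable.** Section 8.5.1 states: "The DLTe population includes ASaT subjects that were observed for safety for 21 days after the first dose of assigned treatment". A treated subject with an earlier DLT also qualifies. The definition does not mention how many planned Cycle 1 doses were received. Table 10 in Section 5.2.1.3 takes as its input the "Number of subjects evaluable for DLT at current dose".

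**Planned exposure.** Section 5.2.5.1 gives MK-1454 on Days 1, 8 and 15 of Cycle 1 in Arms 1 and 2. The Arm 3 schedule in Section 6.1.3 makes Day 8 and Day 15 dosing depend on the cohort. Section 5.2.5 permits interruptions for unrelated medical, surgical or logistical reasons and does not exempt Cycle 1.

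**Under-exposure already covered.** Under item 6 of Section 5.2.2, drug-related toxicity that leads to discontinuation, or to a delay of more than 7 days between Cycle 1 doses, is itself a DLT.

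**Replacement.** Section 5.2.7 says: "Subjects discontinuing within 21 days of the first dose due to reasons unrelated to study treatment will not be considered evaluable for DLTs". It does not say whether this means discontinuing treatment or the trial. Section 5.9 introduces 5.2.7 as the exception for subjects who discontinue from the trial. Section 5.8.1 says: "Discontinuation of treatment does not represent withdrawal from the trial". Section 7.2 requires that, "through 30 days following cessation of treatment, all AEs must be reported by the investigator".

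**Back-fill.** Section 2.1.1 says that DLT information from back-fill subjects "will not be formally included in the mTPI analysis for MTD determination but will be taken into consideration for preliminary RP2D determination". The stopping rule in 5.2.1.3 begins: "After 14 subjects have been enrolled at any of the tested doses (including intermediate doses), dose finding will stop if the mTPI table indicates". Section 8.6.2 says the pool-adjacent-violators algorithm "will be used to estimate the DLT rates across doses in each treatment arm". Neither 5.2.1.3 nor 8.6.2 mentions back-fill.

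**The concern.** DLT is a primary endpoint. The rate at a dose is meant to describe the planned Cycle 1 regimen. A subject who received one of three planned injections, and missed the others for unrelated reasons, has not been exposed to that regimen. Under 8.5.1 the subject still adds one to the denominator and nothing to the numerator. The omission works in one direction only, towards a lower apparent DLT rate, and Table 10 can then read as more permissive.

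The Cohort A and B dose is already fixed. What is at stake is therefore the final DLT reporting in every arm with more than one Cycle 1 dose, and any remaining Arm 3 decision in cohorts dosed on Days 8 and 15. Section 2.1.2 says the Arm 3 dose and frequency carry into Cohort C. Arm 3 cohorts given MK-1454 once per 21-day cycle are not affected by missed Day 8 or Day 15 doses.

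Two readers could also classify the same subject differently under 5.2.7 and 8.5.1.

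**Working it through.** **1. Reproduce Table 10.** Inputs from Section 5.2.1.3: target 30%, ε1 = ε2 = 0.03, prior Beta(1,1). With x DLTs in n evaluable subjects the posterior is Beta(1+x, 1+n−x). For each interval, divide the posterior probability by the interval's width:
- E: P(p<0.27)/0.27
- S: P(0.27<p<0.33)/0.06
- D: P(p>0.33)/0.67

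The largest value gives the decision. DU applies if P(p>0.30) exceeds 0.95. That cut-off is an assumption, since the documents give none. With it, all 78 cells in rows 0 to 6 match. A cut-off of 0.90 misses 7 cells.

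**2. Add one DLT-free, under-exposed subject.**

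| Count | E | S | D | Decision |
|---|---|---|---|---|
| 1/5 | 1.90 | 2.16 | 0.53 | S |
| 1/6 | 2.24 | 2.12 | 0.40 | E |
| 2/10 | 2.24 | 2.56 | 0.36 | S |
| 2/11 | 2.48 | 2.40 | 0.28 | E |
| 2/3 | 0.23 | 0.76 | 1.33 | D |
| 2/4 | 0.47 | 1.32 | 1.19 | S |

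Worked for 1/5, Beta(2,5): P(p<0.27) = 0.5128 and P(p<0.33) = 0.6422, so E = 0.5128/0.27 = 1.90 and S = 0.1294/0.06 = 2.16. Worked for 1/6, Beta(2,6): the values are 0.6035 and 0.7304, so E = 0.6035/0.27 = 2.24 and S = 0.1269/0.06 = 2.12.

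Table 10 shows the same kind of step at 3/5 to 3/6, 4/8 to 4/9, 5/10 to 5/11 and 6/12 to 6/13, each from D to S. A cohort read as 0/3 has only two adequately exposed subjects if one is under-exposed, which is below the three-subject minimum.

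**3. Size of the bias (illustration).** Assume a full-regimen Cycle 1 risk of 30% and one subject in three dosed on Day 1 only. Neither figure is an observed frequency. If r1 is the risk from dose 1 alone, the expected observed rate is (2 × 0.30 + r1)/3, and the chance of 0/3 is 0.70² × (1 − r1).

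| Assumption on r1 | r1 | Expected rate | P(0/3) |
|---|---|---|---|
| Constant per-dose risk, 1 − 0.70^(1/3) | 0.112 | 23.7% | 43.5% |
| 60% of the risk at dose 1 | 0.18 | 26.0% | 40.2% |
| 80% at dose 1 | 0.24 | 28.0% | 37.2% |
| 100% at dose 1 | 0.30 | 30.0% | 34.3% |

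**4. Set 5.2.7 beside 8.5.1.** Take a DLT-free subject who stops treatment after Day 1 for an unrelated reason and is still followed to Day 21.
- If 5.2.7 means treatment: not evaluable under 5.2.7, evaluable under 8.5.1. The sections disagree.
- If 5.2.7 means the trial, as 5.9 suggests: there is no disagreement, but the subject is evaluable under both after one dose.
- A subject who misses doses without discontinuing is evaluable under both on either reading.

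**5. Back-fill.** Section 2.1.1 fixes the count for the MTD decision. Read literally, 8.5.1 (treated subjects observed for 21 days) and 8.6.2 (subjects treated at the MTD or MAD) include back-fill subjects in the reported rate. The term left undefined is the 14 enrolled subjects in 5.2.1.3, because 2.1.1 also lets a cleared dose be back-filled to a total of 14.

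**The case against.** The strongest reply is that most informative under-exposure is already captured, because drug-related discontinuations and long delays are DLTs. What remains is unrelated missed doses. The documents give no frequency for these, and the one-in-three figure above is invented. If acute toxicity follows the first injection, there is no bias at all. All of this stands and limits the point. It does not supply the missing rule: in cohorts of three to six, one subject is enough to move a decision.

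A reader might infer that 8.5.1 and 5.2.7 flatly contradict each other. The documents do not support that. Section 5.9 ties 5.2.7 to discontinuing from the trial, and 5.2.7 itself refers to 8.5.1. The conflict exists on one reading only.

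A reader might also infer that the denominator for the MTD decision is undefined, and point to cases such as 0/3 (escalate) followed by 4 DLTs in 11 back-fill subjects, where 4/14 would read stay. The documents do not support this either. Section 2.1.1 settles that count, so the contrast measures a declared design choice that is not challenged here. Nor is back-fill toxicity hidden from dose selection: 2.1.1 brings it into the preliminary RP2D, and Section 7.1.1.11 requires review of all subjects' safety before the next cohort.

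Finally, an exposure minimum does alter what enters Table 10, and in Arms 1 and 2 it would come after open-label data had informed the dose. That is a fair objection to applying it retrospectively as the main analysis.

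**Conclusion.** The point holds for evaluability. As written, 8.5.1 admits DLT-free subjects with incomplete Cycle 1 dosing in cohorts given MK-1454 on Days 1, 8 and 15, and any bias in the DLT rate is downward. One subject can turn stay into escalate, or de-escalate into stay. In the illustration the expected rate falls from 30% to between 24% and 30%, depending on how much risk the first dose carries. This rests on an assumed 30% risk and an assumed one-in-three share of Day-1-only subjects. The actual frequency is unknown and may be low.

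The tension between 5.2.7 and 8.5.1 is conditional on what discontinuing means, but either reading needs clarifying: one gives a disagreement, the other leaves a one-dose subject evaluable.

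The back-fill matter is a wording clarification only. The change is worth making, with medium confidence in its practical effect.

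**What to change.** 1. **Section 8.5.1:** require a prespecified minimum share of planned Cycle 1 MK-1454 doses, set by the sponsor, before a DLT-free subject is DLT-evaluable. Subjects with a DLT always count.
2. **Sections 5.2.7 and 5.9:** say whether discontinuing refers to treatment or to the trial, and reconcile both with 8.5.1, so that subjects below the minimum for unrelated reasons are non-evaluable and may be replaced.
3. **Application:** use the minimum prospectively for Arm 3 dose decisions. This changes an input to Table 10, not its rules. In the completed Arm 1 and 2 cohorts, use it as a sensitivity analysis of the reported DLT rates.
4. **Secondary clarification:** state in 5.2.1.3 whether the 14 subjects include back-fill, and confirm in 8.6.2 that the reported rates and 80% credible intervals use all DLT-evaluable subjects including back-fill.

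The cost is wording in five sections, a small additional analysis, and an occasional replacement subject in Arm 3 cohorts dosed on Days 8 and 15.

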2.1.2 Part II – Expansion Phase

Initiation of Expansion Cohorts will be staggered based on emerging safety and tolerability data from Part I. Unless deemed medically unsafe by the investigator, all subjects will be required to undergo a biopsy of the lesion to be injected with MK-1454 during the screening period (prior to MK-1454 administration). Subjects with an amenable lesion at the injected site will also undergo tumor biopsies on Cycle 2 Day 1 and optionally on Cycle 3 Day 1, unless deemed medically unsafe by the investigator. The expansion phase of the trial (Figure 3) will evaluate MK-1454 in combination with pembrolizumab 200 mg IV in the following populations:

- Cohort A: Subjects with HNSCC who are anti-PD-1/PD-L1 refractory
- Cohort B: Subjects with either anti-PD-1/PD-L1 treatment-naïve or refractory unresectable locally advanced or metastatic TNBC
- Cohort C: Subjects with other anti-PD-1/PD-L1 treatment-naïve solid tumors with liver metastases

Cohorts A and B will begin at the preliminary RP2D from Arm 2. MK-1454 IT will be administered from Cycle 3 and beyond, in combination with pembrolizumab 200 mg IV Q3W beginning on C1D1). The RP2D dose and the dose for expansion is confirmed to be MK-1454, administered intratumorally to a minimum of 1 lesion per subject per treatment day and a maximum of 3 lesions per subject per treatment day, in combination with pembrolizumab IV.

Cohorts A and B will initiate prior to initiation of Cohort C.

Cohort C will begin at the preliminary RP2D and frequency established from Arm 3.

Treatment duration in each cohort in Part II will be up 35 cycles (approximately 2 years).

Cohorts A and B will each enroll a maximum of 30 subjects, while Cohort C will enroll up to 60 subjects, for a total of up to 120 subjects in the expansion phase. The 60 Cohort C subjects will be enrolled with approximately 15 non-MSI-H CRC subjects, 15 pancreatic ductal adenocarcinoma subjects, and 30 subjects without these specific diagnoses.

Protocol/Amendment No.: 001-08

The trial will be conducted in conformance with GCP.

AEs will be evaluated according to criteria outlined in the NCI CTCAE v4.

[figure not shown]
Specific procedures to be performed during the trial, as well as their prescribed times and associated visit windows, are outlined in the Schedule of Activities - Section 6.0. Details of each procedure are provided in Section 7.0 – Trial Procedures.

